^a Exposure margins were calculated as the ratio of the highest predicted weekly AUC at steady state in children within a given panel to observed weekly steady state exposure of 1) 16,900 $\mu\text{g}\cdot\text{h}/\text{mL}$ from the 6-week rat pivotal toxicity study, 2) 8,540 $\mu\text{g}\cdot\text{h}/\text{mL}$ from the 6-month rat pivotal toxicity study, 3) 87,500 $\mu\text{g}\cdot\text{h}/\text{mL}$ from the 12-week juvenile rat toxicity study, 4) 113,000 $\mu\text{g}\cdot\text{h}/\text{mL}$ from the 6-week monkey pivotal toxicity study and 5) 147,000 $\mu\text{g}\cdot\text{h}/\text{mL}$ from the 6-month monkey pivotal toxicity study.

^b Model-predicted steady-state exposure before the interim analysis and based on the interim analysis, respectively.

^c Model-predicted steady-state exposure based on the interim analysis and assuming 1.6-fold higher exposure with the prefilled syringe compared with the vial formulation.

In healthy volunteers who participated in Study WN40225 (a study designed to compare the bioavailability of RO7239361 at different injection sites), a single dose (50 mg) of RO7239361 following SC administration with a prefilled syringe (PFS) in the arm, thigh, or abdomen was safe and generally well tolerated in healthy adult participants. The PFS achieved approximately 1.6-fold higher exposure than that of the vial formulation (see Investigator's Brochure for further details on Study WN40225 results). If this would also be the case in patients with DMD, the exposure achieved in this study during the OLE phase with the PFS dosage formulation (corresponding to the same dose of 35–50 mg from Panel 3) would still be 1.5 times lower than the exposure achieved with the 180-mg vials in healthy subjects during MAD phase of Study

CN001001. The drug was well tolerated up to doses of 180 mg QW in healthy volunteers.

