1.6.4.1 Pharmacokinetics of RO7239361

RO7239361 achieves peak concentrations *in serum* between 3 and 5 days post-injection and has a terminal half-life of approximately 7 to 10 days across all doses following single SC dose administration (5, 15, 45, 90, and 180 mg). The increase in exposure with dose of RO7239361 appeared to be generally proportional up to 90 mg but was greater than proportional at the highest dose of 180 mg (Study CN001001).

Following multiple RO7239361 administration, T_{max} of RO7239361 was achieved approximately 2–3 days after dosing. The half-life estimates following the last dose were from 10 to 13 days. PK parameters increased in a slightly greater than proportional manner over the explored dose range (15 mg Q1W to 180 mg Q1W) (Study CN001001).

In the current 226 study, the pharmacokinetics of RO7239361 in ambulatory boys with DMD were analyzed using a population-PK approach. The pharmacokinetics of RO7239361 were well characterized using a PD/PK model based on the target-mediated drug disposition concept, and body weight was found to be the only covariate. Steady state was reached after ~12 weeks of Q1W administration. The pharmacokinetics of RO7239361 appear to be dose proportional, considering the between-subject variability. T_{max} of RO7239361 was achieved within 24–30 hours after dosing.

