Upon completion of 24 weeks of double-blind dosing, all subjects will be eligible to enter the OL phase. In this phase, all subjects will receive open-label RO7239361 SC doses, weekly for 48 weeks. Subjects in the OL phase will receive the active dose corresponding to the dose in their originally assigned panel. Dosing in the OL phase may be adjusted based upon emerging safety and tolerability data and/or upon the results of the interim analyses (IAs) of the double-blind data. The schedule of events in the OL phase is described in [Table 5.1-3](#). Subjects who complete the 48-week OL phase, may continue in the OLE phase. Subjects in the OLE phase will continue to receive weekly doses of RO7239361 corresponding to the dose in their originally assigned panel for up to 228 weeks, or until RO7239361 is commercially available, whichever comes first. The study may be stopped earlier if the study is terminated by the Sponsor. In the OLE phase, all subjects will have visits every 12 weeks. The first visit in the OLE phase will occur 12 weeks after OL Week 48 and every 12 weeks thereafter for up to 228 weeks, or until RO7239361 is commercially available.

After approval of Version 6 of Protocol WN40226, and subjects have signed the corresponding updated Informed Consent Form, all participants will switch from the vial formulation to the PFS formulation of RO7239361. Subjects will continue to receive injections from a vial until the PFS becomes available at the site, based on availability of supplies and local approvals.

During the OLE phase, all subjects will switch from the vial formulation to PFS dosage formulation for weekly doses of study drug, corresponding to the same dose in Panel 3 (35 mg dose if a subject's body weight is ≥ 15 kg to ≤ 45 kg and the 50-mg dose if the subject's body weight is >45 kg). Subjects will receive their first dose of RO7239361 from a PFS during a scheduled clinic visit and will return to the clinic for the second PFS dose 1 week later. In addition, subjects will come to the clinic on Day 45 after the switch to the PFS (approximately 2 days after dosing at home) for PK blood sampling. Visits will take place every 12 weeks thereafter, as originally scheduled for the OLE phase.

[figure not shown]
Any subject who discontinues from the study early or who does not enroll in a rollover protocol should enter the follow-up phase of the study. The follow-up phase of the study is up to 24 weeks in length after the last dose.

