3.5 Discontinuation of Subjects following any Treatment with Study Drug

Subjects MUST discontinue investigational product (and non-investigational product at the discretion of the investigator) for any of the following reasons:

- Subject's request to stop study treatment and/or participation in the study
- Any clinical AE, laboratory abnormality or intercurrent illness which, in the opinion of the investigator, indicates that continued participation in the study is not in the best interest of the subject
- Termination of the study by Roche
- Loss of the ability of the parent/legal guardian to freely provide consent through imprisonment or involuntarily incarceration for treatment of either a psychiatric or physical (e.g., infectious disease) illness
- Unblinding a subject for any reason (emergency or non-emergency)
- Inability to comply with protocol
- Discretion of the investigator

Clinical Criteria for Stopping Dose Escalation or Dose Discontinuation:

- Dose escalation will be halted and dosing within a dose panel may be stopped until safety information can be reviewed in the event that:
 - Two (2) or more subjects experience the same severe or very severe adverse event that is considered related to RO7239361, or;
 - Two (2) or more subjects show a decrease in ejection fraction to less than 50% (confirmed by repeat echocardiogram) that is considered related to RO7239361
- Dosing will be paused within a subject until safety information is reviewed and drug-induced liver injury (DILI) is ruled out in the event that:
 - ALT > 5 x baseline AND no corresponding increase in CPK to indicate muscle origin as the reason for the increase in ALT

OR

- ALT > 10 x ULN AND ALT > 2 x baseline AND no corresponding increase in CPK to indicate muscle origin as the reason for the increase in ALT

OR

- Total bilirubin > 2 x ULN

OR

- Symptoms or signs of hepatic inflammation such as nausea, vomiting, right upper quadrant pain, or tenderness with no other immediately apparent possible cause of these symptoms or signs, such as viral gastroenteritis or constipation.

In addition to the above stopping rules, dosing may be paused or halted for a subject or a panel if a review of safety and tolerability data, or the clinical judgment of the investigator, suggest the emergence of a new potentially serious safety signal, including DILI.

The following categories and definitions of intensity as determined by a physician should be

used *assessing the severity of AEs*:

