- ^b The switch to PFS will take place at one of the scheduled clinic visits during the *OLE* phase. After this visit, *subjects* will be required to come to the clinic 1 week later for an additional visit and drug administration and at Day 45 for PK sampling (approximately 2 days after PFS dosing at home). Afterward, visits will take place every 12 weeks as scheduled.
- ^c Body weight will be measured at Day 1 and 12 weeks after the first PFS dose.
- ^d Laboratory tests, GLDH and urine analysis samples will be collected at 12 weeks after the first PFS dose, if not originally scheduled for the regular *OLE* visit.
- ^e Immunogenicity samples will be collected at Day 1 (*prior to the* first PFS dose), Day 45, and 12 weeks after the first PFS dose, if not originally scheduled for regular *OLE* visit).
- ^f Study drug will be administered at Day 1, Day 8, and Week 12.

Table 5.1-5: Post-Study Drug/Placebo Administration Follow-up Procedural Outline

Procedure	Follow-up Week 8 ±1 week	Follow-up Week 16 ±1 week	Follow up Week 24 ±1 week	Notes
Adverse Event Reporting				
Monitor injection site	X	X	X	
Report findings as AEs, as appropriate.
 
It is strongly recommended that site staff take non-subject identifying photographs of moderate to severe injection-site reactions for submission to the Sponsor.

Monitor for previously reported or new onset of non-serious adverse events	X			
Only required if subject discontinued study early due to adverse event or does not participate in a separate rollover study. All non-serious adverse events must be collected until 50 days (5 half-lives) post discontinuation of dosing in the present study. If the subject enters a separate rollover treatment study of RO7239361, the subject's non-serious adverse events will be reported in that study

Monitor for previously reported or new onset of serious adverse events (SAEs)	X			
All SAEs must be collected from the date of subject's written consent until 50 days (5 half-lives) post discontinuation of dosing in the present study. If the subject enters a separate rollover treatment study of RO7239361, the subject's SAEs will be reported in that study.

Safety Assessments				
ECG			X	
Only required for subjects who discontinue study drug due to cardiovascular concerns.

Echocardiogram			X	
Only required for subjects who discontinued study drug due to cardiovascular concerns.

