5.5.1 Pharmacokinetics: Collection and Processing

Table 5.5.1-1 lists the sampling schedule to be followed for the assessment of pharmacokinetics. Further details of blood collection and processing will be provided to the site in the procedure manual and laboratory manual. A PK test may be repeated if it is determined to be inadequate for analysis.

Table 5.5.1-1: Pharmacokinetic Sampling Schedule for RO7239361

Study Day of Sample Collection	Event	Time of Sample Collection, Relative to Time of Dose Administration	RO7239361 Serum Samples
Day 1, double-blind phase	Predose	00:00	X
Day 1, double-blind phase	Postdose	3:00 ± 15 min	X
Day 1, double-blind phase	Postdose	6:00 ± 15 min	X
Day 4, double-blind phase	Post-Day 1 dose	72:00 ± 8 hours	X
Day 5, double-blind phase	Post-Day 1 dose	96:00 ± 8 hours	X
Day 8, double-blind phase	Predose	00:00	X
Day 15, double-blind phase	Predose	00:00	X
Day 22, double-blind phase	Predose	00:00	X
Day 29, double-blind phase	Predose	00:00	X
Day 33, double-blind phase	Post-Day 29 dose	96:00 ± 8 hours	X
Week 12, double-blind phase	Predose	00:00	X
Week 24, double-blind phase	Predose	00:00	X
Week 1, open-label phase	Predose	00:00	X
Week 12, open-label phase	Predose	00:00	X
Week 24, open-label phase	Predose	00:00	X
Week 36, open-label phase	Predose	00:00	X
Week 48, open-label phase	Predose	00:00	X
*Day 1 after switch to PFS in open-label extension phase	Predose	00:00	X
*Day 8 after switch to PFS in open-label extension phase	Predose	00:00	X
*Day 45 after switch to PFS in open-label extension phase	Postdose	48:00	X

Study Day of Sample Collection	Event	Time of Sample Collection, Relative to Time of Dose Administration	RO7239361 Serum Samples
*Week 12 after switch to PFS in open-label extension phase	Predose	00:00	X
Week 60, open-label extension phase	Predose	00:00	X
Week 84, open-label extension phase	Predose	00:00	X
Week 108, open-label extension phase	Predose	00:00	X
Week 132, open-label extension phase	Predose	00:00	X

Table 5.5.1-1: Pharmacokinetic Sampling Schedule for RO7239361

Study Day of Sample Collection	Event	Time of Sample Collection, Relative to Time of Dose Administration	RO7239361 Serum Samples
Week 156, open-label extension phase	Predose	00:00	X
Week 180, open-label extension phase	Predose	00:00	X
Week 204, open-label extension phase	Predose	00:00	X
Week 228, open-label extension phase	Predose	00:00	X

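### After the switch to the prefilled syringe, safety laboratory tests and GLDH are required only at Week 12, and at 7 of 14 possible switch visits this adds no test and leaves no switch-day value

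*Combined protocol and SAP*

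**What the plan says.** Section 3.1 states: "During the OLE phase, all subjects will switch from the vial formulation to PFS dosage formulation for weekly doses of study drug". The dose is the Panel 3 dose, whatever panel the boy came from. Under footnote b of Table 5.1-4 the switch happens at one of the scheduled extension visits; Section 3.1 makes the timing depend on supply and local approvals.

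The switch column of Table 5.1-4 covers Day 1, Day 8, Day 45 and Week 12. For safety laboratory tests, GLDH and urinalysis, footnote d restricts it: "Laboratory tests, GLDH and urine analysis samples will be collected at 12 weeks after the first PFS dose, if not originally scheduled". Immunogenicity, under footnote e, is sampled before the "first PFS dose), Day 45, and 12 weeks after the first PFS dose".

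Blood for PK is taken on Day 1, Day 8 and Week 12 before dosing, and again 48 hours after a dose at "Day 45 after switch to PFS in open-label extension phase" (Table 5.5.1-1). Free myostatin and serum biomarkers are also marked in the switch column, with no restricting footnote.

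Outside the switch column, laboratory tests and GLDH are marked at Weeks 60, 84, 108, 132, 156, 180, 204 and 228. They are not marked at Weeks 72, 96, 120, 144, 168, 192 or 216.

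**The concern.** The switch is a large dose step for boys from the lower panels, yet footnote d ties the extra chemistry to one time point and waives it where that visit is already a laboratory visit. Whether a boy has a value on the day of the step depends on which visit the syringe happens to arrive for.

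What is at stake is liver monitoring. Section 3.5 pauses dosing on criteria such as "ALT > 5 x baseline AND no corresponding increase in CPK to indicate muscle origin", on a second ALT criterion relative to the upper limit of normal, or on raised bilirubin. All of these need a chemistry sample. Section 1.7 says that aminotransferases, bilirubin, GGT and GLDH will be followed. It also reports that 12.5% of treated adults in the multiple-dose study had ALT above 1.25 times the upper limit, mostly at a single time point. One test at Week 12 can miss a transient rise of that kind. If a change does appear at Week 12, a value from the switch day helps to show whether it arose after the switch.

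**Working it through.** The protocol states no figure on this point to reproduce. The check has three parts.

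**1. Which switch visits are affected (Table 5.1-4)**

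Extension visits run every 12 weeks from Week 60 to Week 228, which is 15 visits. Week 228 is end of treatment, so 14 visits can be the switch visit.

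| Switch visit | Laboratory tests on switch day? | Week 12 after switch already routine? | Added by footnote d |
|---|---|---|---|
| 60, 84, 108, 132, 156, 180, 204 (7) | Yes, routine | No | One test at Week 12 |
| 72, 96, 120, 144, 168, 192, 216 (7) | No | Yes (84, 108, 132, 156, 180, 204, 228) | Nothing |

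In the second row the nearest required values are 12 weeks before and 12 weeks after the switch, an interval of 24 weeks. In the first row there is a switch-day value and then nothing until Week 12. With weekly dosing, 12 syringe doses (Days 1 to 78) precede the Week 12 sample.

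**2. Size of the exposure step (Table 1.1-1, interim-based weekly AUC, µg·h/mL)**

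Inputs are 450 (Panel 1), 1,240 (Panel 2), 3,620 (Panel 3 and Expansion) and 5,780 (syringe). The last is predicted "assuming 1.6-fold higher exposure with the prefilled syringe compared with the vial formulation"; 3,620 × 1.6 = 5,792 agrees with it.

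- Panel 1: 5,780/450 = 12.8-fold
- Panel 2: 5,780/1,240 = 4.7-fold
- Panel 3/Expansion: 5,780/3,620 = 1.6-fold

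The 1.6 factor comes from healthy adults. If it were 1.0, the rises would be 3,620/450 = 8.0-fold, 3,620/1,240 = 2.9-fold and 1.0-fold. The step for Panels 1 and 2 therefore does not depend on it. These panels hold about 16 of the 40 planned boys.

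**3. Is Day 45 late enough to be informative?**

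Assume linear accumulation: fraction of the new steady state = 1 − 2^(−t/half-life), with t = 44 days at Day 45 and t = 7 at Day 8. Section 1.6.4.1 gives for adults: "The half-life estimates following the last dose were from 10 to 13 days". For the boys it says: "Steady state was reached after ~12 weeks of Q1W administration". If that means 95% of steady state at day 84, the implied half-life is 84/log2(20) = 19.4 days.

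| Half-life (days) | Day 8 | Day 45 | Day 45 AUC, from Panel 1 | Day 45 AUC, from Panel 2 |
|---|---|---|---|---|
| 10 | 0.384 | 0.953 | 5,528 | 5,565 |
| 13 | 0.311 | 0.904 | 5,270 | 5,345 |
| 19.4 | 0.221 | 0.792 | 4,670 | 4,835 |

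Day 45 AUC = old + fraction × (5,780 − old); for Panel 1 at 13 days, 450 + 0.904 × 5,330 ≈ 5,270. In every case Day 45 exposure is above the 3,620 predicted for the highest vial dose. Day 8 is too early to be much use.

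**The case against.** The best case for the plan is that the interval was chosen and is consistent.

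- **Precedent.** In the open-label phase laboratory tests and GLDH go from Week 1 to Week 12 (Table 5.1-3), and former placebo boys in Panel 3 and the Expansion Panel started active drug there from nothing. The 24-week interval is simply the routine extension interval. This stands, but in the open-label phase every boy had a Week 1 value, and in the double-blind phase tests fell on Days 8, 15 and 29.
- **Existing history.** A boy switching at Week 72 has many earlier on-treatment values, the latest 12 weeks before, and the pause rule refers to baseline or the upper limit of normal. A switch-day value is therefore useful rather than indispensable. That is right; it does not supply the missing values between the switch and Week 12.
- **Timing of the liver signal.** The rat transaminase rise is described as time-dependent and likely rat specific. The 6-week rat no-effect exposure, 16,900, is about 3 times 5,780. Week 12 matches steady state in the boys. This supports keeping Week 12. It does not argue against an earlier sample as well.
- **Safety support and other monitoring.** Adult exposure at 180 mg was about 1.5-fold higher, and the pivotal study reports no new signal. Examinations, vital signs and adverse-event monitoring continue, and the symptom and clinical-judgement grounds for pausing still work. All of this stands and limits the weight of the point.
- **Counting and modelling.** Seven of 14 counts visits, not boys; the share of boys affected could be anything from 0% to 100%. The Day 45 figures assume linearity, although the protocol describes target-mediated disposition. Both limits are accepted.

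**Conclusion.** The concern holds. Footnote d adds no laboratory or GLDH test at 7 of 14 possible switch visits and requires no switch-day value at the same seven. At none of the 14 is there a scheduled test between Day 1 and Week 12. The enumeration follows directly from the visit table and needs no assumption beyond excluding Week 228 as a switch visit.

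The point matters mainly for boys from Panels 1 and 2, with predicted rises of 12.8- and 4.7-fold (8.0- and 2.9-fold without the syringe effect), provided their dose has not already been raised, as the protocol allows. The Day 45 estimate of 79% to 95% of the new steady state rests on linear accumulation and the half-lives stated above.

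This is a gap in extension-phase safety monitoring that should be closed because closing it is easy. It is no sign of known harm, and it does not touch the primary endpoint, which covers the double-blind phase (synopsis) or the double-blind and open-label phases (Section 8.3.1).

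**What to change.** Amend footnote d of Table 5.1-4 so that laboratory tests and GLDH are collected on Day 1 before the first syringe dose, on Day 45, and 12 weeks after the first syringe dose, following the pattern of footnote e. Day 8 can be optional. Urinalysis can stay at Week 12. Summarise post-switch laboratory changes against the Day 1 switch value, by the panel the boy was in before the switch. No dose or stopping rule changes.

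All boys then have a switch-day value (14 of 14 switch visits instead of 7), and the ALT and bilirubin criteria have scheduled data before 12 syringe doses have been given.

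The cost is a one-line change and no new visit. Extra samples are taken at draws already planned: Day 45 for every boy, and Day 1 only where the switch falls at a visit without laboratory tests. The protocol gives no per-visit volumes, so the increase over the approximately 265 mL in Section 3.1 cannot be stated exactly. It covers haematology, serum chemistry and plasma GLDH on at most two occasions and should be small.

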5.3 Safety Assessments

The data from the safety assessments required in this protocol (laboratory tests, ECGs, echocardiograms) will be transferred to Roche from the relevant vendor. The site staff are not required to report these procedures on the CRF. Any findings of potential clinical relevance should be evaluated and managed by the investigator per standard medical/clinical judgment in consultation with the Roche medical monitor. Site staff are required to report to the sponsor on the CRF any AE that is identified during safety assessments.

5.3.1 Echocardiogram

Guidelines for collection of echocardiograms will be provided in the Study Procedures Manual.

A central core lab will perform all imaging analyses. Sites will be informed of quality issues or needs for repeat scanning via queries from the core lab.

Any findings of potential clinical relevance that are not directly associated with the objectives of the protocol should be evaluated and handled by the study investigator as per standard medical/clinical judgment.

Reports (echocardiogram) from the central core lab will be provided to sites for inclusion in the subject's medical record and to provide to subject caregivers. Availability of reports will be determined by the central core lab.

Echocardiogram should be repeated in subjects with new cardiac symptoms.

5.3.2 Electrocardiograms

Guidelines for collection of ECGs will be provided in the Study Procedures Manual.

A central core lab will perform all imaging analyses. Sites will be informed of quality issues or needs for repeat scanning via queries from the core lab.

Any findings of potential clinical relevance that are not directly associated with the objectives of the protocol should be evaluated and handled by the study investigator as per standard medical/clinical judgment.

ECG reports from the central core lab will be provided to sites for inclusion in the subject's medical record and to provide to subject caregivers. Availability of reports will be determined by the central core lab.

ECG should be repeated in subjects with new cardiac symptoms.

